### 8.3.2. Additional Diagnostic Imaging

If a subject is called back for further diagnostic assessment, the additional FFDM views will be recorded on the CRF. In addition, any other imaging which the subject undergoes will be recorded (e.g., ultrasound or magnetic resonance imaging [MRI]).

## 8.4. Biopsy Procedures

Biopsy(ies) will be completed for subjects whose screening mammography (DBT and/or FFDM) and subsequent diagnostic work-up results provide a clinical indication for biopsy. No biopsies will be performed solely for research purposes as part of this study.

Percutaneous and/or open surgical breast interventions will proceed as per standard of care at the recruiting site. A record of breast lesion characteristics, including the type of lesion and approximate size based on histology and surgical findings, and location of the lesion by left or right breast and within a breast quadrant will be recorded on the CRF. The interpretation of the local pathologist will be recorded on the CRF.

For benign/negative histopathology results, the site radiologist will review the subject's imaging and histopathology findings for concordance, per the site's standard of care, and results will be captured on a CRF. Histologic concordance with imaging for negative or benign lesions will be considered truth for non-cancer status. If surgical excision is recommended even after

concordance between imaging and histopathology, the resulting histopathology from surgical excision may be collected as part of the study. If available, one-year follow-up data will be used to determine truth status in lieu of concordance assessments.

Subjects who have negative or benign histology findings that are discordant with imaging shall be followed-up per the site's standard of care. If rebiopsy is recommended, the histology findings and concordance assessment of the rebiopsy will be used to determine the subject's cancer status. If rebiopsy is not recommended, the subject will be followed at approximately one year (10-16 months).

## 8.5. Follow-up (Month 10-16) Procedures

All subjects will be followed at approximately one year (10-16 months) unless positive cancer status is histologically determined or imaging and histology are deemed concordant prior to one year follow-up. For any subject who undergoes one-year follow-up procedures, the follow-up results will be considered truth for non-cancer or cancer status.

Applicable subjects should be scheduled to complete one year follow-up by month 15, allowing for one month (until month 16) to reschedule subjects unable to attend or to collect previously completed one-year follow-up images completed at another clinical site. If no suspicious findings are observed at one-year follow-up, this will be considered truth of non-cancer status. If suspicious findings are observed, the subject will undergo standard of care diagnostic work-up, and results will be considered truth for non-cancer or cancer status.

If the initial GE FFDM and/or DBT imaging or incidental standard of care procedures conducted prior to one-year follow-up reveals suspicious findings that could indicate breast cancer, the subject will undergo standard of care diagnostic work-up (e.g. clinically indicated MRI, ultrasound, biopsy, or other exams). Cancer status should be reported using all available clinical information, according to the Investigator's medical judgment. Positive cancer results from diagnostic work-up, biopsy and histology will be considered truth of positive cancer status, and no additional follow-up will be required once truth is established.

## 8.6. Incidental Findings

If any unexpected atypical or abnormal findings unrelated to the study aims (breast cancer identification) are identified during this study that may incidentally indicate other diseases or other unknown conditions, these cases will be reported to the Site Principal Investigator. If the Site Principal Investigator determines that these findings are medically significant in his or her medical judgment, he or she will notify the subject and refer her for further follow-up outside of this study according to the standard of care at the investigational site. Follow-up for incidental findings is not required by this study, but relevant images and data resulting from examinations related to incidental findings may be provided to the Sponsor, at the discretion of the Principal Investigator, if determined to be relevant to study conduct or integrity of study results.

## 8.7. Withdrawal and Discontinuation Criteria

### 8.7.1. Subject Withdrawal Rules

The subject's medical care shall take precedence over any research imaging or other procedures associated with the study. If it is determined during the exam that the research imaging will in any way negatively impact required clinical care, the subject shall be withdrawn from the study.

Each subject is free to withdraw from the study at any time. Investigator(s) also have the right to withdraw subjects from the study in the event of illness, AEs, SAEs or other reasons concerning the health or well-being of the subject, or in the case of lack of cooperation.

If a subject withdraws (or is withdrawn), all efforts will be made to complete and report the observations up to the time of withdrawal. A complete final evaluation at the time of the subject's withdrawal should be made and an explanation given on the CRF given as to why the subject is withdrawing or being withdrawn from the study. If the reason for withdrawal is a clinical AE or SAE, monitoring will continue until the outcome is evident. The specific event or test result(s) must be recorded on the CRF.

In the event the subject experiences pain, undue discomfort, or destabilizing vital signs that is observed by visual inspection or via monitoring equipment, or requests to discontinue study procedures, the study procedures will be stopped immediately, and the appropriate response will be taken according to the standard of care at the investigational site.

A subject may withdraw from study participation at any time, for any reason without consequence. The study staff may withdraw a subject at any time for any reason. There shall be no negative repercussions to the subject. The reasons for withdrawal and discontinuation for any subject shall be recorded. These will be reported to the Sponsor. The EC/IRB should be notified per their notification of subject withdrawal policy.

Subjects withdrawn after consent is signed and randomized read order is given will be counted as enrolled subjects up until the time of withdrawal, and will be considered in reporting total enrolled subjects in this study per the populations defined in Section 10.1.2. - Study Populations.

## 9. TRAINING PLAN

### 9.1. Training Plan for Research Device/Product

Training will be provided to study staff on the use of device system(s), as needed. Study staff that will be operating the device(s) during subject procedures may be required to receive additional training above that required by other study staff. The Sponsor will provide instructions for use of the device and, as necessary, subsequent training, at the Sponsor's discretion or upon request by the site.

### 9.2. Training Plan for Protocol

Study staff will be trained on the study protocol and study procedures, including completion of Informed Consent Forms (ICFs), Case Report Forms (CRFs), and other study documentation.

Training will also be provided to ensure appropriate storage and handling of images and data. All study staff will be required to be trained on Good Clinical Practice (GCP) guidelines per ISO 14155: 2011.

A record of all formal training attendance and dates conducted will be stored in the Site Regulatory Binder and provided to the Sponsor for inclusion in the Sponsor's Clinical History File (CHF).

### 9.3. Reader Training

All study staff assessing images for this study will be qualified radiologists at the investigational site(s), and reads will be performed according to the standard of care at the investigational site. All readers will be trained on the study protocol and recording of data on case report forms (CRFs) prior to reading images. Determinations made by site radiologists based on DBT and FFDM images collected in this study may be included in the subject's regular medical record.

## 10. DATA ANALYSIS AND STATISTICS

### 10.1. Statistical Analysis Methods

#### 10.1.1. Sample Size Justification

The projected sample size is determined by the need to accrue at least 120 cancer cases and 250 non-cancer cases for the overall GE Healthcare SenoClaire® - GE Breast Tomosynthesis (DBT) development program. To achieve these overall accrual targets, the data from this study will be pooled with data from other studies (e.g. ADAPT-BX and ADAPT-Enrich).

In this study, for an enrollment of 250 screening subjects, it is assumed, based on the GE-190-001 experience, that about 185 (75%) will complete the study with a normal 1-year follow-up. Approximately 2% are expected to have a proven cancer either at screening or during follow-up which will provide an estimated 6 cancer cases.

Based on the GE-190-003 experience, for an enrollment of 275 subjects recommended for breast biopsy, approximately 33% are expected to have a proven cancer and 33% will have a benign lesion. So, at least 90 cancer cases and 90 benign cases are expected to be accrued in the ADAPT-BX study.

In the ADAPT-ENRICH study, for a target enrollment of 200 subjects recommended for breast biopsy, it is assumed, based on the GE-190-003 experience, that approximately 33% are expected to have a proven cancer. Thus, at least 66 cancer cases are expected from the ADAPT-ENRICH study.

In the combined protocols (ADAPT-SCR, ADAPT-BX, and ADAPT-ENRICH), it is expected that at least 120 cancer cases and 250 non-cancer cases will be accrued for the overall GEHC DBT development program.

The data from this study will be pooled with data from other subjects who will be recruited from other sources (e.g. ADAPT-BX). If necessary, data from other sources may also be included to

achieve the required number of cancer and non-cancer cases. The accrued screening images will be used in a blinded image evaluation to analyze the diagnostic performance of SenoClaire® -GE Breast Tomosynthesis (DBT) compared to FFDM through receiver operating characteristic (ROC) analysis, sensitivity, specificity, recall rate and other analyses.

No statistical analyses are included as part of this study. A descriptive summary will be provided for the data collected in this study.

#### **10.1.2. Study Populations**

The *Efficacy Population* will consist of those subjects meeting the study inclusion/exclusion criteria with no protocol violations judged to affect the ability to evaluate the subject, whose DBT and FFDM images are diagnostically evaluable, and whose mammography images are available for the independent blinded evaluation regardless of the image quality. Non-available images will include:

- those lost due to corrupted media or inability of site to transport to image review center;
- subjects where no images are acquired.

The Sponsor will make any decisions regarding whether any subjects or any individual values belonging to a subject will be excluded from the evaluations when a protocol violation is considered to have a negative impact on the scientific aspects and interpretation of the study results. The reason(s) for any exclusion(s) will be documented in the study report.

The *Safety Population* will include all subjects enrolled into the study.

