### 5.3. Study Endpoints

#### 5.3.1. Primary endpoints

The primary endpoint will be the site's diagnosis of cancer status (positive or negative/benign) for each subject based on DBT and FFDM at baseline (0 months) and 10-16 months, and/or (if clinically indicated) histology and surgical findings. Histologic concordance with imaging will be assessed for benign lesions, when applicable, and DBT and FFDM image sets will be assessed using BI-RADS® scores.

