### 7.4. Procedures for Enrollment

All subjects must satisfy all the inclusion criteria and none of the exclusion criteria defined in the protocol. Subjects must sign and date the informed consent form prior to completing protocol-specific procedures. The Investigator may discuss with the Sponsor any subject who does not strictly meet the inclusion/exclusion criteria but who is thought to be otherwise appropriate for the study; if the Sponsor and Investigator agree that inclusion of the subject would not affect the scientific or ethical aspects of the study, the Sponsor may provide a written exception for the subject. In this case, the details of the exception will be recorded on the case report form (CRF). Each subject will be assigned a randomized order for reading of their DBT and FFDM images such that approximately half of the subjects will have their DBT images interpreted first and the other half will have their FFDM images interpreted first. A subject will be considered enrolled when determined eligible, informed consent is signed, and randomized read order is assigned, whether or not the subject undergoes study procedures.

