#### **10.1.3. Subject Disposition and Characteristics**

Subjects enrolled/randomized, imaged, and withdrawn will be summarized overall and by site and imaging modality. Descriptive statistics and summaries will be provided for demographics, medical histories, image acquisition, lesions and findings and BI-RADS® assessments.

Specific subgroups of interest include stratification by the following variables:

- Age;
- Menopausal status; and
- Breast density.

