#### **10.1.4. Adverse Events**

Adverse events will be reported from the time the subject enters the imaging suite for study procedures until the time the subject leaves the imaging suite after the study procedure. Device-related adverse events (AEs) and serious adverse events (SAEs) reported by subjects within 30 days of imaging (only those reported by subjects will be considered, and no separate 30-day follow-up is planned), and device malfunctions occurring in the safety population will be

summarized with subject counts overall and by modality (DBT and FFDM). Additionally, individual subject listings will be provided to detail all AE/SAE information collected.

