#### **10.3. Handling of Missing Data**

There will be no imputation of missing data and collected data will be analyzed as is.

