#### **10.4. Pass/Fail Criteria of the Study**

No statistical criteria for success are defined for this accrual study, which will be considered successful if subject number and truth data accrual targets are met, without consideration for subsequent analysis results.

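### Must the plan name the women counted in the cancer-status summary and in the accrual verdict?

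*Combined protocol and SAP*

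**What the plan says.** - **Populations (Section 10.1.2).** The Efficacy Population holds eligible women "with no protocol violations judged to affect the ability to evaluate the subject, whose DBT and FFDM images are diagnostically evaluable" and whose images can be supplied to the blinded readers. It does not require an established cancer status. The Safety Population is everyone enrolled.
- **Use of the populations.** Section 10.1.4 ties the adverse event summaries and "device malfunctions occurring in the safety population" to the Safety Population. The Efficacy Population is not mentioned again after its definition. Section 10.1.3 says "Subjects enrolled/randomized, imaged, and withdrawn will be summarized overall and by site and imaging modality" and lists further descriptive summaries, without naming a population and without listing cancer status.
- **Primary endpoint (Section 5.3.1).** "The primary endpoint will be the site's diagnosis of cancer status (positive or negative/benign) for each subject".
- **Missing data (Section 10.3).** "There will be no imputation of missing data and collected data will be analyzed as is".
- **Who is enrolled.** Under Section 7.4 a woman counts once she is eligible, has consented and has a read order, "whether or not the subject undergoes study procedures". Under Section 8.7.1, women withdrawn after that point "will be counted as enrolled subjects up until the time of withdrawal, and will be considered in reporting total enrolled subjects in this study".
- **Success (Section 10.4).** The study "will be considered successful if subject number and truth data accrual targets are met". The section prints no number.
- **Purpose.** Section 5.1 says that no hypothesis is tested. Section 10.1.1 promises only a descriptive summary.

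**The concern.** A population that is defined and never used suggests that a link to the outputs was lost. The primary endpoint has two categories, and a woman who misses the 10 to 16 month visit and has no histology fits neither. The missing data rule does not say whether she stays in the denominator. Section 10.4 then bases success on targets it does not state, in a study where a woman who was never imaged still counts as enrolled.

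If the gap mattered, two results of this protocol would depend on an unstated choice: the cancer-status summary, and whether the study met its only success criterion. With nearly a quarter of women possibly lacking a status, the choice of denominator would be visible in the report.

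**Working it through.** **Inputs (Section 10.1.1):** 250 enrolled; about 185 (75%) with a normal one-year follow-up; about 2%, given as 6 women, with proven cancer; 90 cancers and 90 benign cases expected from ADAPT-BX; 66 cancers from ADAPT-ENRICH; pooled targets of 120 cancers and 250 non-cancers.

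**1. The plan's own figures.** 0.75 × 250 = 187.5, against 185 printed (185/250 = 74.0%). 0.02 × 250 = 5, against 6 printed (6/250 = 2.4%). Both agree to rounding.

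**2. Women without a status by these two routes.** 185 + 6 = 191, and 250 − 191 = 59, which is 59/250 = 23.6%. Using the counts implied by the percentages in place of the printed ones moves the remainder between 250 − 188 − 6 = 56 and 250 − 185 − 5 = 60. The figure 59 is derived here and is not printed in the protocol.

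**3. Effect of the denominator.** Non-cancer: 185/250 = 74.0% or 185/191 = 96.9%. Cancer: 6/250 = 2.4% or 6/191 = 3.1%.

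**4. Why 59 is a ceiling.** The 185 counts only normal follow-ups. Section 8.4 also accepts concordant benign histology as proof of non-cancer, and Section 8.5 accepts a benign work-up. The documents do not say how many women reach a status in these ways. The values below are assumptions that show the range.

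| Of the 59, with a status (assumed) | Non-cancer, all enrolled | Non-cancer, status known |
|---|---|---|
| 0 | 185/250 = 74.0% | 185/191 = 96.9% |
| 15 | 200/250 = 80.0% | 200/206 = 97.1% |
| 30 | 215/250 = 86.0% | 215/221 = 97.3% |
| 45 | 230/250 = 92.0% | 230/236 = 97.5% |

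The contrast narrows but remains. What matters is whether anything in the protocol rests on it.

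**5. What rests on the percentage.** Section 5.1 rules out a hypothesis test, and Section 10.1.3 lists no cancer-status proportion. The endpoint will appear in the general descriptive summary as counts, and the counts of cancers and non-cancers do not depend on the denominator. Section 10.3 forbids imputation, so a woman of unknown status cannot be moved into either category. She can only be reported as missing.

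**6. The success criterion.** Section 10.4 joins subject number and truth data, so both must be met. Subject number reads naturally as enrollment, which Section 7.4 defines. A shortfall in truth data cannot be hidden by an enrollment count. The Synopsis assigns the 250 screening cases to this study together with other sources, so nothing requires 250 women with truth from this study alone. The relevant figures stand in Section 10.1.1:

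- Cancers: 6 + 90 + 66 = 162 expected, against 120.
- Non-cancers: 185 + 90 = 275 expected, against 250. The margin is 25, or 25/275 = 9.1%. The sum leaves out any benign cases from ADAPT-ENRICH and any concordant benign cases from this study.

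**7. Membership of the Efficacy Population.** Women admitted under a Section 7.4 exception do not strictly meet the entry criteria, and Section 10.1.2 requires that those criteria be met. On a plain reading they are outside the population. The two phrases about images also agree: a non-diagnostic examination is out, and a poor but readable one stays in.

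**The case for a change.** The strongest case for a change is that the endpoint and the success criterion belong to this protocol, so pointing to ADAPT-BIE does not settle them. The study is open-label. Section 10.2 lets the sponsor look at accumulating data at any time, and Section 10.1.2 lets the sponsor exclude women or single values for protocol violations with no rule on timing or masking. Section 15.1 says that the images are meant for a regulatory submission, where the path from enrolled woman to usable case should be traceable. The remedy would cost little: a few words and one table row.

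Part of this stands. The Efficacy Population has no stated use, the endpoint has no place for an unknown status, and Section 10.4 does not point to Section 10.1.1.

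The rest does not carry a change. Traceability is largely provided for: enrolled, imaged and withdrawn women are summarized (Section 10.1.3), reasons for withdrawal are recorded (Section 8.7.1), and reasons for exclusion go into the study report (Section 10.1.2). The definition refers to the blinded evaluation, so when exclusions are fixed relative to the blinded reads is a matter for ADAPT-BIE and its review charter, which are separate documents and cannot be judged from this one. This study makes no comparison of DBT with FFDM that a late exclusion could distort. Low cost alone is not a reason to amend when no result changes.

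**Conclusion.** No change to the plan follows. The protocol leaves out a detail that analysts fill sensibly: a descriptive table of cancer status would show the number enrolled, the number in each category and the number not established, and Section 10.4 would be read with the figures in Section 10.1.1.

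The size is at most about 59 of 250 women (23.6%; 56 to 60 depending on how the planning figures are read). That ceiling moves the cancer share between 2.4% and 3.1%, and the non-cancer share between 74.0% and 96.9%. It does not alter the counts, and no test or claim in this protocol uses the shares.

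The conclusion rests on three readings of the text: the study stays descriptive, the two parts of the success criterion are judged separately, and the pooled targets may draw on other sources as the Synopsis and Section 10.1.1 say. It would need another look if this study were to make an inferential claim from the proportion with cancer, or if success were judged on a single undefined count.

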#### **10.1.3. Subject Disposition and Characteristics**

Subjects enrolled/randomized, imaged, and withdrawn will be summarized overall and by site and imaging modality. Descriptive statistics and summaries will be provided for demographics, medical histories, image acquisition, lesions and findings and BI-RADS® assessments.

Specific subgroups of interest include stratification by the following variables:

- Age;
- Menopausal status; and
- Breast density.

#### **10.1.4. Adverse Events**

Adverse events will be reported from the time the subject enters the imaging suite for study procedures until the time the subject leaves the imaging suite after the study procedure. Device-related adverse events (AEs) and serious adverse events (SAEs) reported by subjects within 30 days of imaging (only those reported by subjects will be considered, and no separate 30-day follow-up is planned), and device malfunctions occurring in the safety population will be

summarized with subject counts overall and by modality (DBT and FFDM). Additionally, individual subject listings will be provided to detail all AE/SAE information collected.

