### 12.3. Management of Adverse Event Reporting

Any adverse events will be recorded in the subject's study record and the Adverse Event Case Report Form. The following information should be obtained:

- Description of Event
- Date of onset and resolution
- Intensity (mild, moderate, severe)
  - **Mild:** Symptom(s) barely noticeable to the subject or does not make the subject uncomfortable. The AE does not influence performance or functioning. Prescription drugs are not ordinarily needed for relief of symptom(s).
  - **Moderate:** Symptom(s) of a sufficient severity to make the subject uncomfortable. Performance of daily activities is influenced. Treatment of symptom(s) may be needed.
  - **Severe:** Symptom(s) of a sufficient severity to cause the subject severe discomfort. Treatment for symptom(s) may be given.
- Serious (yes/no)
- Relationship to device (unrelated, possibly related, probably related)

- **Unrelated:** The adverse event is reasonably expected to be related to (or caused by) a concurrent illness, effect of another device/drug or other cause, and is unlikely related to the investigational product.
- **Possibly related:** The adverse event is reasonably expected to be related to the investigational product, and an alternative etiology is equally or less likely compared to the potential relationship to investigational product.
- **Probably related:** There is a strong relationship to investigational product, or recurs on re-challenge, and another etiology is unlikely, or there is no other reasonable medical explanation for the event.

- Treatment given and/or action taken (procedure stopped, withdrawn from study, no action)
- Anticipated (yes/no)

Adverse events will be reported to the local EC/IRB per their policy.

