## **12.4. Management of Serious Adverse Event and Unanticipated Adverse Device Effect Reporting**

All SAEs and or UADEs will be documented as above and reported in writing to the Sponsor within 72 hours of knowledge of the event. The Investigator shall submit the Adverse Event Case Report Form and GEHC\_GQP\_10.07.005\_F002 Site Notification and Assessment of Serious and Unexpected Adverse Events (DOC0910335) with redacted supporting documentation to SAE mailbox.

If the event resulted in the death of a subject, the event shall also be reported via telephone to the Sponsor within 24 hours of knowledge of the event. SAEs will be reported to the local EC/IRB per their policy.

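### Section 10.1.4 counts device-related AEs and SAEs within 30 days of imaging only when the subject reports them, so the safety table can undercount and disagree with its own listing

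*Combined protocol and SAP*

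**What the plan says.** Section 10.1.4 has three parts that matter here.

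- AEs are reported from entry into the imaging suite "until the time the subject leaves the imaging suite after the study procedure". No limit is placed on who notices them.
- The summary then covers device-related AEs and SAEs "reported by subjects within 30 days of imaging", with the qualification that "only those reported by subjects will be considered, and no separate 30-day follow-up is planned". These are shown as subject counts, overall and by modality, in the safety population.
- Separately, "individual subject listings will be provided to detail all AE/SAE information collected".

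Other sections set no limit on source. Section 5.3.3 defines the safety endpoint as device-related AEs, SAEs and malfunctions arising during the study. Section 12.3 opens with "Any adverse events will be recorded" and names the study record and the CRF. Section 12.4 requires every SAE and UADE to be "reported in writing to the Sponsor within 72 hours of knowledge of the event". It adds a faster route for deaths: "If the event resulted in the death of a subject, the event shall also be reported via telephone". Section 10.1.2 puts all enrolled subjects in the safety population, and Section 7.1 caps enrollment at 250.

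**The concern.** The parenthesis in Section 10.1.4 contains two rules. One says that nobody will contact women at 30 days, which makes surveillance passive. That is a reasonable choice for a mammography accrual study and is not disputed here. The other says whose report counts. Passive surveillance does not need the second rule, because an event can reach the site without active follow-up and without the woman volunteering it.

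The gap is a practical one. The foreseeable effects in Section 12.1 are mostly visible on the skin: bruising, irritation, abrasions and tears. Sections 8.3.2 and 8.4 describe call-back imaging and biopsy, where staff may see the woman again, possibly inside 30 days. A lesion that staff note and she does not mention fails the counting rule.

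At stake is the internal consistency of the only safety output the study plans. Section 5.3.3 states that no other clinical safety assessment is made, and Section 15.1 says the image data are intended for a regulatory submission.

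**Working it through.** The plan states no figure on this point, so there is none to reproduce. The check is to apply the counting rule, the recording rules and the listing rule to the same events.

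| Device-related event | Recorded or reported (12.3, 12.4) | In listing (10.1.4) | In summary count (10.1.4 as written) |
|---|---|---|---|
| In the imaging suite, noticed by staff | Yes | Yes | Presumably intended, but see below |
| After the visit, within 30 days, reported by the subject | Yes | Yes | Yes |
| After the visit, within 30 days, seen by staff at recall or biopsy, not mentioned by the subject | Yes, under 12.3 | Yes, once collected | No |
| SAE within 30 days, known from a treating clinician or relative | Yes, to the Sponsor within 72 hours | Yes | No |
| Death within 30 days | Yes, also by telephone within 24 hours | Yes | No, unless the subject had reported the event earlier |

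Three points follow.

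1. **Direction.** Let *s* be the number of women with a device-related event that they reported themselves within 30 days. Let *o* be the number whose only such event is known from another source. The table shows *s*, and the listing supports *s* + *o*. The difference is *o*, which cannot be negative, so the rule can lower the count but never raise it.

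2. **Size per omission.** With the safety population at its ceiling of 250, the proportion falls by *o*/250. For *o* = 1 this is 1/250 = 0.4 percentage points. The documents give no event rate and no rate of return visits within 30 days, so *o* itself cannot be estimated from them.

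3. **Events in the suite.** The imaging visit lies inside the 30-day window, and the sentence with the source restriction is the only one that says what is summarized. Taken literally, it would also drop a tear seen only by the technologist, although Section 8.2 has subjects monitored for AEs at imaging. That is unlikely to be intended, but the current sentence does not rule it out.

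No other sentence in Section 10.1.4 brings events from other sources back into the counts.

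**The case against.** The strongest reply is that the parenthesis is loosely drafted and means only that post-visit surveillance is passive. The odd result for events in the suite supports that reading of intent. It does not settle the matter, because the text says only subject-reported events are considered, and an analyst programming the table has to follow the words or depart from them.

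The second reply is that nothing is lost. This largely stands. SAEs, UADEs and deaths reach the Sponsor under Section 12.4, and the listings carry no source limit. For non-serious events after the visit it depends on sites applying Section 12.3 as written, without importing the suite window from Section 10.1.4. With at most 250 women, a careful reader of the listing would see the mismatch, and Section 10.1.5 allows changes to the analysis to be explained in the study report.

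Two stronger readings are tempting, and the documents support neither.

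- A reader might infer that the rule hides deaths. A post-visit death could indeed fall outside the count, but it would be telephoned to the Sponsor and listed. A device-related death after mammography is also remote, given the effects foreseen in Section 12.1. Skin events seen by staff are the realistic case.
- A reader might infer that one omitted event changes the study's conclusion. The exact 95% interval is 0 to 1.46% for 0/250 and 0.01% to 2.21% for 1/250. These overlap almost entirely, and the plan calls for neither. Section 5.1 tests no hypothesis, Section 10.1.1 plans only a descriptive summary, and Section 10.4 ties success to accrual. No safety threshold exists for a count to cross.

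**Conclusion.** The point holds as a reporting defect of modest weight that should be corrected. As written, Section 10.1.4 filters the 30-day counts of device-related AEs and SAEs by who reported them. That does not match the recording and reporting triggers in Sections 12.3 and 12.4, the endpoint in Section 5.3.3, or the listing promised in the same section. The consequence is a one-directional undercount in a descriptive table, 0.4 percentage points per woman omitted at 250 enrolled, and a table that may not agree with its listing or the SAE file.

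This rests on the literal reading of the parenthesis. If the sponsor meant only passive surveillance, the wording still needs to say so. The number of events affected is unknown and may be zero.

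**What to change.** In Section 10.1.4, replace the restriction to subject-reported events with wording such as: *device-related AEs and SAEs occurring within 30 days of imaging and known to the site or Sponsor from any source (subject, staff, treating clinician, medical record or family)*. Keep the statement that no separate follow-up contact is made at 30 days. Add the source of each report as a column in the individual listing.

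The new wording also covers events seen by staff in the suite. It leaves the 30-day period unchanged. Because Section 5.3.3 speaks of events during the study, a cross-reference there to the Section 10.1.4 window would align the two.

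The cost is one sentence and one listing column. No visit, contact or clinical procedure is added, since Section 12 already requires the recording and reporting. The downside for the sponsor is that the event count may be slightly less favourable.
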